TITLE OF STUDY: A Comparison of Surgical Conditions between Deep vs Moderate Neuromuscular Blockade with Rocuronium in patients undergoing Endolaryngeal Procedures

OBJECTIVES:

Primary Study Objective: To compare the proportion of patients with a score of excellent for surgical conditions of deep Neuromuscular Blockade (NMB) (TOF 0, PTC 1–2) versus moderate NMB (TOF 1–2) using Rocuronium in patients undergoing Endolaryngeal Procedures

Secondary Study Objective:

1. To describe the proportion of patients who are Ready to Discharge from operating room, in both the sugammadex 4 mg/kg after deep Neuromuscular Blockade (NMB) (TOF 0, PTC 1–2) group and sugammadex 2 mg/kg after moderate NMB (TOF 1–2) group .
2. To describe the proportion of patients who are Ready to Discharge from Post Anesthetic Care Unit (PACU), in both the sugammadex 4 mg/kg after deep Neuromuscular Blockade (NMB) (TOF 0, PTC 1–2) group and sugammadex 2 mg/kg after moderate NMB (TOF 1–2) group .
3. To assess frequency of clinical signs of early recovery during Endolaryngeal Procedures both deep NMB and Moderate NMB.
Clinical signs of early recovery:
 - a. Airway pressure alarm
 - b. Movement of Vocal cords on Laryngeal Video monitor
 - c. Movement of the abdomen
 - d. Change of End Tidal CO₂

STUDY DESIGN: Overview: A multi-center, open-label, assessor-blinded, randomized, parallel intervention trial.

Number of Study Centers: This study will be conducted at 6 centers throughout Thailand.

Duration of Participation: Each subject will participate in the study for approximately up to 1 day from the time the subject signs the Informed Consent Form (ICF) through the last data collection point. The subjects will be observed for the post-operative complication for 1 day after study drug cessation.

Duration of Study: The total study duration is 16 months (4 months of institutional review board submission/approval, 8 months of enrollment period, 3 months of study analysis and reporting)

Key Inclusion/Exclusion Criteria:

Inclusion criteria:

1. Male or female aged 18 – 60 years; ASA I-III.
2. Subjects have been planned for elective endolaryngeal Procedures (Direct Laryngoscopy with laser (micro-)surgery in patients with endolaryngeal lesions.

Exclusion criteria:

1. Any renal impairment (CrCL < 80 ml/ min)
2. Any hepatic impairment; Child Pugh A, B or C
3. BMI > 30 kg m²
4. Known or suspected generalized neuromuscular disorders
5. Allergies to Rocuronium, Sugammadex, Sevoflurane, Propofol, fentanyl used during general anesthesia
6. Hypersensitivity to the active substance or to any of the excipients
7. Female patient who are pregnant and breastfeeding.
8. Patient with poor Glasgow Coma Score and mental derangement who is unable to give informed

consent.

9. Patients with tracheostomy tube.

INVESTIGATIONAL PRODUCT, DOSE, MODE OF ADMINISTRATION:

Investigational product:

After initial doses of **0.6 mg** Rocuronium, a continuous infusion can be initiated to maintain 0 responses to train-of-four (TOF) stimulation or 1-2 responses to Post-Tetanic Count (PTC) (Deep NMB). The pump rate will vary and depends on the PTC value. The initial pump rate will be set at 0.5 mg/kg per hour. In case of a deviation from the required PTC value the pump rate can be increased or decreased. This was left to the discretion of the attending anaesthetist. Deep NMB should be maintained throughout the operation.

The infusion of Rocuronium will be discontinued and Sugammadex will be given 4 mg/kg at the end of surgery, which is from deep NMB (PTC = 1-2).

Reference Product:

After evidence of early spontaneous recovery (< 10% of control T1) from initial doses of **0.4 mg** rocuronium, a continuous infusion can be initiated to maintain 1 to 2 responses to train-of-four stimulation (Moderate NMB). The initial pump rate will be set at 0.5 mg/kg per hour. In case of a deviation from the required TOF value the pump rate can be increased or decreased. This was left to the discretion of the attending anaesthesiologist. Moderate paralysis should be maintained throughout an operation.

At the end of surgery, the infusion of Rocuronium will be discontinued and Sugammadex 2 mg/kg via bolus injections will be administered at least reappearance of T2.

STATISTICAL METHODS:

All subjects entered into paper-based Case Report Forms (CRFs) will be considered as part of the enrollment population, and the quality of their data will be assessed for further analyses. The evaluable population will consist of all subjects whose data meet the inclusion criteria. The criteria for exclusion from the evaluable population will be set forth in the Data Analysis Plan prior to commencement of any analyses, and will include such criteria as minimum data points required.

Data Set to be Analyzed:

Baseline Patients Characteristics:

We will describe the data distribution of each collected variable. We will characterize subjects in both groups by demographics, comorbidities, clinical characteristics i.e. neuromuscular weakness grading, and distribution of ASA Classification pattern. Categorical variables will be summarized by frequency and percent while continuous variables will be summarized by the mean, median, standard deviation, and range.

Clinical Outcomes:

The data analysis will be based on the intent-to-treat approach. Categorical variables will be compared using the Fisher's exact test while continuous variables will be compared using the student's t-test or Mann-Whitney U test, depending on the sample distribution.

The level of statistical significance for all analyses is set at 0.05. All comparisons will be made using an alpha level of 0.05.

Sample Size: By using 80% power and 1-sided $\alpha=0.05$, we performed sample size calculation for the proportional outcome. Based on data from the BLISS study¹², the proportion of patients with a score of Excellent on the Surgical Rating Score (SRS) among subjects who receive deep NMB with Rocuronium is approximately 99%, while this proportion for patients who received moderate NMB with atacurium followed by mivacurium was lower (82%). The calculated subjects is required 36 subjects per arm. Since we expect 13% of withdrawal from the study¹³, we need to inflate the total sample size to 80 subjects (40 subjects per arm)

Efficacy Analysis:

1. Primary Efficacy endpoints:

The Proportion of patients who have a surgical conditions score of excellent (total score = 8-9) will be compared between the Moderate NMB and Deep NMB groups.

2. Secondary outcome

- 1) The proportion of patients who are ready to be discharged from post- operative care, defined as Modified Aldrete's score ≥ 9 , at 0, 15, 30,60, 90 minutes after reach of TOF > 0.9 will be summarized.
- 2) The proportion of patients who are ready to be discharged from the operating room, defined as TOF > 0.9 at time of tracheal extubation, at 1, 3, 5, 10 minutes after finish of Procedures will be summarized.
- 3) The frequency of patients with clinical signs of early recovery during Endolaryngeal Procedures will be compared between the deep NMB and Moderate NMB arms.

Safety Analysis: This is a post-marketing study of treatment outcomes associated with surgical conditions and readiness of discharge from Post-Operating Care Unit(PACU) with Rocuronium and Sugammadex. Responsibility for clinical follow-up resides with the prescribing physician. Therefore, reporting of AEs and SAEs as they occur in clinical practice should follow the established Procedures for approved, marketed drugs in compliance with applicable laws and regulations. This applies to AEs and SAEs noted by the prescribing physician through clinical observation, clinical monitoring, diagnostic Procedures or other applicable methods.

Interim Analysis: N/A

Section #3- Core Protocol

2.1.1 List the objectives.

1.1) Primary Efficacy Objective:

1. To compare the proportion of patients with a score of excellent for surgical conditions of deep Neuromuscular Blockade (NMB) (TOF 0, PTC 1–2) versus moderate NMB (TOF 1–2) using Rocuronium in patients undergoing Endolaryngeal Procedures.

Surgical Conditions will be rated using a four-point surgical condition scale by one dedicated Surgeon from each center.

- TOF = Train of Four
- PTC = post-tetanic counts

1.2) Secondary Objective:

1. To describe the proportion of patients who are Ready to Discharge from operating room, in both the sugammadex 4 mg/kg after deep Neuromuscular Blockade (NMB) (TOF 0, PTC 1–2) group and sugammadex 2 mg/kg after moderate NMB (TOF 1–2) group .

**Readiness to discharge:* Readiness to Discharge from operating room, which is defined by train of Four ratio > 0.9 at any time after finish of Procedures.

2. To describe the proportion of patients who are Ready to Discharge from PACU*, in both the sugammadex 4 mg/kg after deep Neuromuscular Blockade (NMB) (TOF 0, PTC 1–2) group and sugammadex 2 mg/kg after moderate NMB (TOF 1–2) group .

- **Readiness to discharge from PACU is defined below.*
 - Modified Aldrete's scoring system is used for determining when patients can be safely discharged from the postanesthesia care unit (PACU) to either the postsurgical ward or to the second stage (Phase II) recovery area.
 - Modified Aldrete's score: A score ≥ 9 is required for discharge.

3. To assess frequency of clinical signs of early recovery during Endolaryngeal Procedures both deep NMB and Moderate NMB..

Clinical signs of early recovery:

- a. Airway pressure alarm
- b. Movement of Vocal cords on Laryngeal Video monitor
- c. Movement of the abdomen
- d. Change of End Tidal CO₂

3) Other objectives: -

- To assess time from the Post-anesthesia Care Unit (PACU) admission to PACU discharge ready

- To assess time readiness to discharge from operating room, which is time from finish of Procedures to train of Four ratio > 0.9.

- To assess Proportion of patients at risk of Post-Operative Residual Curarization (PORC) (defined as TOF < 0.9) at 1,3,5, 10minutes after finish of Procedures and

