2.1 Objectives & Hypotheses

	
at arrival ,15, 30, 60, and 90 minutes during Post-Operative Care Unit stay.
 
 - Proportion of patients who have a surgical conditions score in each category (Excellent, good, fair and poor). 
 • Surgical conditions will be rated using a four-point surgical rating scale (SRS) by an anesthesiologist. (not attending physicians) every 15 minutes and every change seen or surgeon's complaint. • The SRS will be also rated by an expert anesthesiologist and expert ENT surgeon from VDO recorder every change seen at a vocal cord. -To assess intubating condition in patients who has endotracheal insertion. This will be assessed by anesthesiologists right after finishing intubation.. 
2.1.2 List the clinical hypotheses.
 
 1. Sustained deep NMB for the duration of surgery in patients undergoing Endolaryngeal Procedures has better surgical conditions compared to those receiving moderate NMB when rated using a four-point surgical rating condition scale (SRS). 2. The frequency of Clinical Signs of Early recovery during an Endolaryngeal Procedures are less frequent in the Deep NMB group compared to the Moderate NMB.

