Before discharging from Post-Operative Care Unit, patients will be assessed “time readiness to discharge from PACU” by evaluating Modified Aldrete recovery score. The score will be measured at least 15 minutes interval.

MODIFIED Aldrete recovery score¹⁴

Parameter	Description of patient	Score
Activity level	Moves all extremities voluntarily/on command	2
	Moves 2 extremities	1
	Cannot move extremities	0
Respirations	Breathes deeply and coughs freely	2
	Is dyspneic, with shallow, limited breathing	1
	Is apneic	0
Circulation (blood pressure)	Is 20 mm Hg > preanesthetic level	2
	Is 20 to 50 mm Hg > preanesthetic level	1
	Is 50 mm Hg > preanesthetic level	0
Consciousness	Is fully awake	2
	Is arousable on calling	1
	Is not responding	0
Oxygen saturation as determined by pulse oximetry	Has level >90% when breathing room air	2
	Requires supplemental oxygen to maintain level >90%	1
	Has level <90% with oxygen supplementation	0

Maximum total score is 10; a score of ≥ 9 is required for discharge.

- Main goals are controlling postoperative pain, controlling nausea and vomiting, and reestablishing normothermia prior to discharge
- Majority of patients can meet discharge criteria within 60 minutes in the PACU, no demonstrable benefit from a mandatory minimum duration of PACU care
- Outpatients who meet the above discharge criteria may be “fast-tracked” to phase 2 recovery, similarly inpatients who meet the same criteria may be transferred directly from the OR to their ward. This is required less extensively monitoring.

Statistical Methods:

All statistical analysis will be performed by STATA or SPSS, depends on availability.

Baseline Patients Characteristics:

We will describe the data distribution of each collected variable. We will characterize subjects in both groups by demographics, comorbidities, clinical characteristics i.e. neuromuscular weakness grading, and distribution of ASA Classification pattern. Categorical variables will be summarized by frequency and percent while continuous variables will be summarized by the mean, median, standard deviation, and range.

Clinical Outcomes:

The data analysis will be based on the intent-to-treat approach. All comparisons will be made using an alpha level of 0.05

1. Primary Efficacy endpoints:

The Proportion of patients who have a surgical conditions score of excellent will be compared between the Moderate NMB and Deep NMB groups using Fisher’s Exact test

2. Secondary outcome

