Based on data from the BLISS study¹⁵, the proportion of patients a with a score of Excellent on the Surgical Rating Score (SRS) among subjects who receive deep NMB with Rocuronium is approximately 99%, while this proportion for patients who received moderate NMB with atacurium followed by mivacurium was lower (82%)..

By using 80% power and 1-sided $\alpha=0.05$, we performed sample size calculation by using the following formula.

For the proportion outcomes

$$n = \frac{2(\bar{p})(1 - \bar{p})(Z_{\beta} + Z_{\alpha})^2}{(p_1 - p_2)^2}$$

All expected primary outcome, secondary outcomes and calculated sample sizes are shown in the following table

	Deep NMB	Mode rate NMB	Sample size
Primary outcome			80% Power
- Proportion of Excellent	99%	82%	36/arm

Since we expect 13% of withdrawal from the study¹⁶, we need to inflate the total sample size to **80 subjects (40 subjects per arm)**.

As mentioned in the earlier session, the first five Procedures performed in conformance with this protocol will not be used for data analysis; thus, the Procedures will be practiced five times each center before data collection starts.

Therefore, the total enrolled patients are 110 patients.

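### The stated 80% power belongs to an uncorrected z-formula; the planned Fisher's exact test gives 77% with 40 evaluable per arm and 67% after the planned 13% withdrawal

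*Combined protocol and SAP*

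**What the plan says.** The sample size paragraph appears in the Synopsis (Statistical Methods, Sample Size) and again in section 2.7 (Sample size calculation).

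- **Basis:** "By using 80% power and 1-sided" alpha of 0.05. The assumed proportions with an excellent score are 99% (deep block) and 82% (moderate block).
- **Formula:** section 2.7 says "we performed sample size calculation by using the following formula" and prints a pooled two-proportion z-formula without continuity correction. The result is 36 per arm.
- **Withdrawal:** "Since we expect 13% of withdrawal from the study", and then "we need to inflate the total sample size to 80 subjects (40 subjects per arm").
- **Test:** section 2.7, Clinical Outcomes, says that the primary proportion "will be compared between the Moderate NMB and Deep NMB groups using Fisher’s Exact test".
- **Significance level:** the Synopsis says "The level of statistical significance for all analyses is set at 0.05", without a side. Section 2.7 repeats the 0.05 level, also without a side.
- **Direction:** the first clinical hypothesis in section 2.1.2 is directional: sustained deep block "has better surgical conditions compared to those receiving moderate NMB".

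No power is given for Fisher's exact test anywhere.

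**The concern.** The power claim and the test do not belong together. The z-formula describes an approximate test that uses nearly all of its 5% error rate. Fisher's exact test conditions on the margins. With a rate near 99% and about 40 per arm, only a few tables are likely, so the test's attainable levels are coarse and its real error rate lies well below 5%. Power falls with it.

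A reader of the plan would put the risk of missing a true 99% versus 82% difference at 20%. If the real risk is a quarter to a third, a null result means less than the plan suggests. The missing side adds a second problem, because a borderline result could be called significant or not depending on a choice that the analysis text does not make.

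**Working it through.** **Inputs** (Synopsis, Sample Size; section 2.7): p1 = 0.99, p2 = 0.82, one-sided alpha 0.05, power 80%, equal allocation, 13% withdrawal, 40 per arm.

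**1. The plan's own figure.** Mean rate = (0.99 + 0.82)/2 = 0.905, and (1.645 + 0.842)² = 6.183.

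n = 2 × 0.905 × 0.095 × 6.183 / 0.17² = 36.8.

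The common variant, with pooled variance under the null and unpooled under the alternative, gives 35.7. So 36 reproduces for an uncorrected approximate test, whose approximate power at 36 per arm is 80.3%. The choice between 36 and 37 is not counted as an error. With a continuity correction the one-sided figure is 47.

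**2. Power of the planned test.** Exact power is the sum of Bin(x; n, 0.99) × Bin(y; n, 0.82) over all tables with Fisher p ≤ 0.05. At 40 per arm, one-sided:

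| Deep excellent (x) | P(x) | Significant if moderate is at most | P(that) | Product |
|---|---|---|---|---|
| 40 | 0.669 | 35 | 0.870 | 0.582 |
| 39 | 0.270 | 33 | 0.597 | 0.161 |
| 38 | 0.053 | 32 | 0.434 | 0.023 |
| 37 or fewer | | | | 0.001 |

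The total is 0.768. The same sum for other sizes gives:

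| Evaluable, deep/moderate | One-sided 0.05 | Two-sided 0.05 |
|---|---|---|
| 35/35 | 67.3% | 51.6% |
| 35/34 | 69.2% | 64.7% |
| 36/36 | 69.4% | 54.1% |
| 40/39 | 74.8% | 74.8% |
| 40/40 | 76.8% | 63.5% |
| 42/42 | 79.9% | 67.7% |
| 43/43 | 81.3% | 69.6% |
| 50/50 | 89.0% | 79.7% |
| 51/51 | 89.8% | 81.0% |
| 49/48 | 87.0% | 85.9% |

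The two-sided p-value orders tables by probability. The two-sided column moves sharply with exact arm sizes, because with equal arms the mirror-image table doubles the p-value and with unequal arms it may not.

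**3. Size needed for 80% with Fisher's test, equal arms.** One-sided: 43 evaluable, and 43/0.87 = 49.4, so 50 enrolled per arm. Two-sided: 51 evaluable, and 51/0.87 = 58.6, so 59 per arm.

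**4. Side of the test.** Take 40/40 versus 35/40 excellent. One-sided p = C(40,5)/C(80,5) = 0.0274. With equal arms the two-sided p is twice that, 0.0547. The two readings fall on opposite sides of 0.05.

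**5. Withdrawal.** 36/0.87 = 41.4, so 42 per arm; even 36 × 1.13 = 40.7, so 41. Keeping 36 of 40 is a loss of 4/40 = 10%. After 13%, 80 × 0.87 = 69.6 remain, about 35 per arm. Correcting this alone does not rescue the claim, since 42 per arm with no loss gives 79.9%.

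**The case against.** **The arithmetic is sound for its formula, and sizing by z-formula before a Fisher analysis is common.** True. The fault is a mismatch between sizing method and test, not a miscalculated 36. The plan still attaches 80% to an analysis that does not deliver it.

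**The assumed 99% is only approximate.** This carries weight for the no-loss figure. At 40 per arm one-sided, power is 81.7% if the deep rate is 99.5%, 80.8% if the moderate rate is 81%, and 72.0% if the deep rate is 98.5%. The three-point gap at 40 per arm is therefore within the precision of the inputs. The after-loss gap is not: 35 per arm gives 72.4% at 99.5% and 62.5% at 98.5%.

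**The 67% assumes that withdrawn patients have no primary score.** This is also fair. The score is given straight after the operation, the study lasts about a day, and the analysis is by intention to treat, so withdrawals may cost few scores. If all 40 are scored, 77% applies. But the plan inflates for withdrawal and defines an evaluable population, so the after-loss figure answers its own assumption.

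**The only side stated is one-sided, and the hypothesis is directional.** Nothing contradicts a one-sided test. However, a directional hypothesis does not settle which p-value is reported, and the analysis text is silent.

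**More patients were analysed.** The tables at the end of the document show 49 deep and 48 moderate, where power at the planned rates is 87% one-sided and 86% two-sided. That limits the practical consequence but does not correct the written justification for 80.

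**Conclusion.** The concern holds. With the test the plan names, on the one-sided basis it documents and at its own rates, power is 76.8% with 40 evaluable per arm and 67.3% with 35. At the 36 per arm said to be required it is 69.4%. The 80% is missed even with no withdrawals. If the test is two-sided, the equal-arm figures are 63.5% and 51.6%, though these depend heavily on exact arm sizes.

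The results rest on 99% versus 82%. The lower figure also assumes that 13% of patients give no primary score. The side of the primary test is unstated where the analysis is described, and this can change the conclusion in a borderline case. The withdrawal shortfall (40 instead of 42) is a minor slip. The type I error of the test is unaffected. The matter should be corrected, but it does not threaten validity.

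**What to change.** 1. State the side of the primary test once, in the same words in the Synopsis (Clinical Outcomes and Sample Size) and in section 2.7. Because results are already appended, say whether the side was fixed before the data were seen.
2. Replace the bare 80% with the power of the named test. For example: with Fisher's exact test at one-sided 0.05 and rates of 99% and 82%, power is 77% with 40 evaluable per arm and 67% with 35 per arm. If two-sided is chosen, the equal-arm figures are 64% and 52%, with a note that they change markedly when the arms differ by one patient.
3. Say either that 40 per arm allows for losing 10% of those enrolled, or that 13% requires 42 per arm.

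The cost is a few sentences in the Synopsis and section 2.7 and a less favourable stated power. No extra patients and no change of test are needed.

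### The step from 36 to 40 per arm does not deliver the stated 13% withdrawal allowance: from 36 it needs 42, and 40 covers 10%

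*Combined protocol and SAP*

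**What the plan says.** The calculation appears in the Synopsis (Statistical Methods, Sample Size) and again in section 2.7 (Sample size calculation). Its assumptions are:

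- Proportion rated excellent: "among subjects who receive deep NMB with Rocuronium is approximately 99"%, against "moderate NMB with atacurium followed by mivacurium was lower (82"%) in the comparator group of the cited study.
- Error rates: "By using 80% power and 1-sided" alpha of 0.05.
- Method: section 2.7 says "we performed sample size calculation by using the following formula" and prints a two-proportion formula that uses one pooled variance.

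The Synopsis gives the result as "The calculated subjects is required 36 subjects per arm", and the table in section 2.7 repeats 36 per arm. Both places then expect 13% withdrawal, citing an earlier study, and conclude "we need to inflate the total sample size to 80 subjects (40 subjects per arm").

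Section 2.7 adds five practice procedures per center, which are left out of the analysis: "Therefore, the total enrolled patients are 110 patients". The Synopsis gives six centers. Neither place shows how 36 became 40, and neither states another rule for the allowance.

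**The concern.** An allowance for withdrawal has one job: after the expected loss, the number left should still meet the requirement. Here the requirement (36), the loss (13%) and the enrolled number (40) are all stated, and the three do not agree. One division shows it.

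At stake is whether the justification for the primary comparison can be relied on as written. A reader would take it that 13% withdrawal has been provided for. If that loss occurred among patients needed for the primary outcome, the trial would fall below the number that the plan says it needs.

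**Working it through.** **Inputs.** p1 = 0.99 and p2 = 0.82, so the mean is 0.905 and the difference 0.17; Z for one-sided 0.05 = 1.6449; Z for 80% power = 0.8416; withdrawal 13%; six centers with five practice procedures each. All except the Z values are in the Synopsis and section 2.7.

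**Step 1: the base number.**

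- Printed formula: n = 2 × 0.905 × 0.095 × (0.8416 + 1.6449)² / 0.17² = 36.79, which rounds up to 37. Rounding the Z values in the usual ways gives 36.6 to 36.8, so rounded inputs do not explain 36.
- Standard two-proportion formula (pooled variance under the null, unpooled under the alternative): n = [1.6449 × √(2 × 0.905 × 0.095) + 0.8416 × √(0.99 × 0.01 + 0.82 × 0.18)]² / 0.17² = 35.72, which rounds up to 36.

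So the stated 36 is one below the printed formula's answer and equals the standard formula's. At 36 per arm, power is 79.2% by the first and 80.3% by the second.

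**Step 2: the allowance, from the plan's own 36.**

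- Per arm: 36/0.87 = 41.4, so 42 per arm and 84 in total.
- On the total: 72/0.87 = 82.8, so 83.
- The common but incorrect shortcut: 36 × 1.13 = 40.68, so 41 per arm and 82 in total.

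Rounded up, none of these gives 40 per arm.

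**Step 3: what 40 per arm does cover.**

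- From 36: 1 − 36/40 = 10%.
- At 13% withdrawal: 40 × 0.87 = 34.8 per arm, below 36.

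**Step 4: the same steps from 37.** 37/0.87 = 42.5, so 43 per arm and 86 in total; 40 per arm covers 1 − 37/40 = 7.5%.

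**Step 5: total enrolment.** Practice procedures: 6 × 5 = 30. As stated, 80 + 30 = 110. With the 13% allowance applied, 84 + 30 = 114 from 36, or 86 + 30 = 116 from 37.

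**Step 6: effect on power with 34.8 per arm.**

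- Printed formula: Z = 0.17/√(2 × 0.905 × 0.095/34.8) − 1.6449 = 0.774, so 78.0%.
- Standard formula: 79.1%.
- The planned test, Fisher's exact, by full enumeration at 35 per arm under 99% and 82%: about 67% one-sided and 52% two-sided.

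The first two figures measure the effect of the allowance error within the plan's own approach. The third shows that neither is the power of the planned test.

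**The case against.** Five counter-arguments deserve weight.

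- **The base number is acceptable.** This stands. A standard formula with the same inputs gives 36, so 36 alone should not be called an error. A reader might infer that the trial is plainly three per arm short; that rests on 37. From the plan's stated requirement the shortfall is two per arm.
- **The origin of 40 is unknown.** This also stands. A reader might infer that the sponsor used a 10% allowance, since 36/0.90 = 40. But 36 × 1.13 = 40.68 cut down to 40 explains the figure equally well, just as 36.79 cut down gives 36. The documents do not show the step. Either way, 40 does not provide 13%.
- **Withdrawal may cost little primary data.** The surgeon scores the primary outcome once, as soon as the procedure ends; participation lasts about a day; and the analysis is by intention to treat. Losses after scoring would not remove the endpoint, so 34.8 assumes that every withdrawal loses the score. That limits the consequence. But the plan itself chose to allow for 13%, and the Synopsis also defines an evaluable population with exclusions.
- **More patients appear to have been analyzed.** The results tables at the end of the document show groups of 48 and 49, above 42 and 43. A reader might infer from the arithmetic that the completed trial was too small on the plan's terms; these tables do not support that. Nor do they correct the written justification.
- **The total of 110 is correct addition.** It is: 80 + 30. It carries the shortfall forward and is not a second error.

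**Conclusion.** The point holds for the allowance step. On the plan's own figures of 36 per arm and 13% withdrawal, 42 per arm are needed; 40 covers 10% and leaves 34.8 at 13%. The shortfall is two per arm and four in total (three and six if the printed formula's 37 is used). It rests on the ordinary meaning of an allowance, with the required number remaining after the expected loss, and on withdrawals counting as lost primary data.

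The consequence is small. Power falls to 78.0% by the printed formula or 79.1% by the standard one, against a target of 80%. That is a mis-stated figure worth correcting, not a threat to the trial's validity.

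A reader might also take 78% as the trial's power after withdrawal. The documents do not support that: the figure comes from a one-sided normal approximation, whereas section 2.7 names Fisher's exact test for the primary comparison. The choice of test and sidedness is a separate and larger question, and settling it would change the base number.

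**What to change.** In the Synopsis sample size paragraph and in section 2.7 (Sample size calculation), replace the claim that 40 per arm allows for 13% withdrawal. State instead that:

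- 40 per arm allows for about 10% withdrawal from a requirement of 36, or 7.5% from the 37 given by the printed formula;
- 13% withdrawal would leave about 35 evaluable per arm, below the stated requirement.

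In the same edit, either give 37 as the printed formula's result or name the formula that yields 36. If a power figure at 13% withdrawal is included, label 78% as coming from the printed normal-approximation formula only, and say that it is not the power of Fisher's exact test.

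No patients are added, no procedure changes, and 80 and 110 can stand as enrolment figures. The cost is about two sentences in each place and a stated allowance that is less favorable than the present one. If the test or its sidedness is revised, redo these figures at the same time so that they are not superseded.
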